Study intervention: Portia (0.03 mg EE/ 0.15 mg LNG)		Х	Х	Х	Х	Х	Х	Х	Х	Х	Х	Х	Х	Х					
Study intervention: GSK3640254 200 mg								Χ	Х	Х	Х	Х	Х	Х					
Trough PK sampling: EE and LNG						D9						Х	Х						PK sample collected before dosing.

Procedure	Check-in	I	Run-ir	1					Tre	eatmen	t					Wash	out 1		Notes
	D -4	D -3	D -2	D -1	D 1	D 2-9	D 10 	D 11	D 12	D 13	D 14-18	D 19	D 20	D 21	D 22	D 23	D 24 	D 25	
Serial PK sampling: EE and LNG							X	Х						X	X	X	X		PK samples will be collected predose and after dosing at 15 and 30 minutes and 1, 1.5, 2, 3, 4, 7, 12, and 24 hours relative to Day 10 dosing. The 24-hour post-dose sample should be taken prior to dosing on Day 11. PK samples will be collected predose and after dosing at 15 and 30 minutes and 1, 1.5, 2, 3, 4, 7, 12, 24, 48, and 72 hours relative to Day 21 dosing.
Trough PK sampling: GSK3640254												Χ	Χ						PK sample collected before dosing.
Serial PK sampling: GSK3640254														Х	Х	Х	X	Х	PK samples will be collected predose and after dosing at 1, 2, 2.5, 3, 3.5, 4, 4.5, 5, 6, 8, 12, 24, 48, 72, and 96 hours relative to Day 21 dosing.
PD sampling: LH, FSH, progesterone					Χ		Х	Х						Х	Х				Samples collected before dosing.
AE review		←====================================								====									
SAE review	←====	====	====	=====	====	=====	=====	====	====	=====	======	=====	=====	=====	=====	=====	=====	==>	

Procedure	Check-in		Run-ir	1		Treatment										Wasl	nout 1		Notes
	D -4	D -3	D -2	D -1	D 1	D 2-9	D 10 	D 11	D 12	D 13	D 14-18	D 19	D 20	D 21	D 22	D 23	D 24 	D 25	
Concomitant medication review	←====		=====		====	=====		====	====	=====	======	=====	====	=====	=====		=====	==>	

AE = adverse event; D = Day; C-SSRS = Columbia Suicide Severity Rating Scale; ECG = electrocardiogram; EE = ethinyl estradiol; FSH = follicle-stimulating hormone; LH = luteinizing hormone; LNG = levonorgestrel; PD = pharmacodynamic; PK = pharmacokinetic; SAE = serious adverse event.

- 1 Washout period refers to follow-up period. See 208135 Protocol Clarification dated 10-Jun-2019.
- 2 Assessments performed on Day 10 will be considered Baseline for GSK3640254 dosing.
- 3 Evaluations scheduled for Day 24 will also be performed for participants who discontinue early.

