# 11.6. Appendix 6: Division of AIDS (DAIDS) Table for Grading the Severity of Adult and Pediatric Adverse Events

# 11.6.1. Laboratory Values

Laboratory abnormalities will be graded according to the DAIDS grading table Version 2.1, July 2017. Laboratory results are converted to use SI units; only the numeric part of the criteria will be used. If for a laboratory parameter there are multiple grades sharing the same criteria, the maximum grade will be used.

HEMATOLOGY				
	Grade 1	Grade 2	Grade 3	Grade 4
Absolute Lymphocyte Count, Low (cell/mm³; cells/L) > 5 years of age (not HIV infected)	600 to < 650 0.600 × 10  to < 0.650 × 10 	500 to < 600 0.500 × 10  to < 0.600 × 10 	350 to < 500 0.350 × 10  to < 0.500 × 10 	< 350 < 0.350 × 10 
Absolute Neutrophil Count, Low (cells/mm³; cells/L) > 7 days of age	800 to 1,000 0.800 × 10  to 1.000 × 10 	600 to 799 0.600 × 109 to 0.799 × 109	400 to 599 0.400 × 10  to 0.599 × 10 	< 400 < 0.400 × 10 
Hemoglobin, Low (g/dL; mmol/L)	10.0 to 10.9	9.0 to < 10.0	7.0 to < 9.0	< 7.0
≥ 13 years of age (male only)	6.19 to 6.76	5.57 to < 6.19	4.34 to < 5.57	<4.34
Hemoglobin, Low (g/dL; mmol/L)	9.5 to 10.4	8.5 to < 9.5	6.5 to < 8.5	< 6.5
≥ 13 years of age (female only)	5.88 to 6.48	5.25 to < 5.88	4.03 to < 5.25	< 4.03
Platelets, Decreased (cells/mm³; cells/L)	100,000 to < 125,000 100.000 × 10  to < 125.000 × 10 	50,000 to < 100,000 50.000 × 10  to < 100.000 × 10 	25,000 to < 50,000 25.000 × 10  to < 50.000 × 10 	< 25,000 < 25.000 × 10 
White Blood Cell, Decreased (cells/mm³; cells/L) > 7 days of age	2,000 to 2,499 2.000 × 10  to 2.499 × 10 	1,500 to 1,999 1.500 × 10  to 1.999 × 10 	1,000 to 1,499 1.000 × 10  to 1.499 × 10 	< 1,000 < 1.000 × 10 

Clinical Chemistry				
	Grade 1	Grade 2	Grade 3	Grade 4
Albumin, Low (g/dL; g/L)	3.0 to < LLN 30 to < LLN	≥ 2.0 to < 3.0 ≥ 20 to < 30	< 2.0 < 20	NA
Alkaline Phosphatase, High	1.25 to < 2.5 × ULN	2.5 to < 5.0 × ULN	5.0 to < 10.0 × ULN	≥ 10.0 × ULN
Alanine Aminotransferase, High	1.25 to < 2.5 × ULN	2.5 to < 5.0 × ULN	5.0 to < 10.0 × ULN	≥ 10.0 ULN
Amylase (Total), High	1.1 to < 1.5 × ULN	1.5 to < 3.0 × ULN	3.0 to < 5.0 × ULN	≥ 5.0 × ULN

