Aspartate Aminotransferase, High	1.25 to < 2.5 × ULN	2.5 to < 5.0 × ULN	5.0 to < 10.0 × ULN	≥ 10.0 × ULN
Bicarbonate, Low (mEq/L; mmol/L)	16.0 to < LLN 16.0 to < LLN	11.0 to < 16.0 11.0 to < 16.0	8.0 to < 11.0 8.0 to < 110.	< 8.0 < 8.0
Direct Bilirubin, High > 28 days of age	NA	NA	> ULN with other signs and symptoms of hepatotoxicity	> ULN with life-threatening consequences (e.g., signs and symptoms of liver failure)
Total Bilirubin, High > 28 days of age	1.1 to < 1.6 × ULN	1.6 to < 2.6 × ULN	2.6 to < 5.0 × ULN	≥ 5.0 × ULN
Calcium, High (mg/dL; mmol/L)	10.6 to < 11.5	11.5 to < 12.5	12.5 to < 13.5	≥ 13.5
≥ 7 days of age	2.65 to < 2.88	2.88 to < 3.13	3.13 to < 3.38	≥ 3.38
Calcium, Low (mg/dL; mmol/L)	7.8 to < 8.4	7.0 to < 7.8	6.1 to < 7.0	< 6.1
≥ 7 days of age	1.95 to < 2.10	1.75 to < 1.95	1.53 to < 1.75	< 1.53
Creatine Kinase, High	3 to < 6 × ULN	6 to < 10 × ULN	10 to < 20 × ULN	≥ 20 × ULN
Creatinine, High Choose the method that selects for the higher grade	1.1 to 1.3 × ULN	> 1.3 to 1.8 × ULN OR Increase to 1.3 to < 1.5 × participant's baseline	> 1.8 to < 3.5 ULN OR Increase to 1.5 to < 2.0 × participant's baseline	≥ 3.5 × ULN OR Increase of ≥ 2.0 × participant's baseline
Glucose Fasting, High (mg/dL; mmol/L)	110 to 125 6.11 to < 6.95	> 125 to 250 6.95 to < 13.89	> 250 to 500 13.89 to < 27.75	≥ 500 ≥ 27.75
Glucose, Low (mg/dL; mmol/L)	55 to 64	40 to < 55	30 to < 40	< 30
≥ 1 month of age	3.05 to < 3.55	2.22 to < 3.05	1.67 to < 2.22	< 1.67
Lipase, High	1.1 to < 1.5 × ULN	1.5 to < 3.0 × ULN	3.0 to < 5.0 × ULN	≥ 5.0 × ULN
Cholesterol, Fasting, High (mg/dL; mmol/L) ≥ 18 years of age	200 to < 240 5.18 to < 6.19	240 to < 300 6.19 to < 7.77	≥ 300 ≥ 7.77	NA
Triglycerides, Fasting, High (mg/dL;	150 to 300	> 300 to 500	> 500 to < 1.000	> 1,000
mmol/L)	1.71 to 3.42	> 3.42 to 5.7	> 5.7 to 11.4	> 11.4
Phosphate, Low (mg/dL; mmol/L)	2.0 to < LLN	1.4 to < 2.0	1.0 to < 1.4	< 1.0
> 14 years of age	0.65 to < LLN	0.45 to < 0.65	0.32 to < 0.45	< 0.32

Clinical Chemistry					
	Grade 1	Grade 2	Grade 3	Grade 4	
Potassium, High (mEq/L; mmol/L)	5.6 to < 6.0	6.0 to < 6.5	6.5 to < 7.0	≥ 7.0	
	5.6 to < 6.0	6.0 to < 6.5	6.5 to < 7.0	≥ 7.0	
Potassium, Low (mEq/L; mmol/L)	3.0 to < 3.4	2.5 to < 3.0	2.0 to < 2.5	< 2.0	
	3.0 to < 3.4	2.5 to < 3.0	2.0 to < 2.5	< 2.0	
Codium High (mFg/L mmg/L)	146 to < 150	150 to < 154	154 to < 160	≥ 160	
Sodium, High (mEq/L; mmol/L)	146 to < 150	150 to < 154	154 to < 160	≥ 160	
Sodium, Low (mEq/L; mmol/L)	130 to < 135	125 to < 130	121 to < 125	≤ 120	

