# 11.9.5. Safety Tables

Safety:	Tables				
No.	Population	IDSL / Example Shell	Title	Programming Notes	Deliverable [Priority]
Advers	e Events (AEs)				 
2.1.	Safety	AE1CP	Summary of Adverse Events by System Organ Class and Preferred Term		SAC
2.2.	Safety	AE1CP	Summary of Drug-Related Adverse Events by System Organ Class and Preferred Term		SAC
2.3.	Safety	AE3	Summary of Common (>=5%) Adverse Events by Overall Frequency		SAC
2.4.	Safety	AE15	Summary of Common (>=5%) Non-serious Adverse Events by System Organ Class and Preferred Term (Number of Subjects and Occurrences)		SAC
2.5.	Safety	AE16	Summary of Serious Adverse Events by System Organ Class and Preferred Term (Number of Subjects and Occurrences)		SAC
2.6.	Safety	AE5A	Summary of Adverse Events by System Organ Class and Preferred Term and Maximum Intensity		SAC
2.20.	Safety	AE1CP	Summary of Adverse Events of Special Interest		SAC
Labora	tory: Chemistry	/			·
2.7.	Safety	LB1	Summary of Clinical Chemistry Changes from Baseline		SAC
2.21.	Safety	LB1	Summary of Clinical Chemistry Values		SAC
2.8.	Safety	LB16	Summary of Clinical Chemistry Results by Maximum Grade Increase Post-Baseline Relative to Baseline		SAC
Labora	tory: Hematolo	gy			·
2.9.	Safety	LB1	Summary of Hematology Changes from Baseline		SAC

Safety:	Tables				
No.	Population	IDSL / Example Shell	Title	Programming Notes	Deliverable [Priority]
2.22.	Safety	LB1	Summary of Hematology Values		SAC
2.10.	Safety	LB16	Summary of Hematology Results by Maximum Grade Increase Post-Baseline Relative to Baseline		SAC
Labora	tory: Urinalysis	;			 
2.11.	Safety	UR3	Summary of Urinalysis Dipstick Results		SAC
2.12.	Safety	LB1	Summary of Urine Concentration Changes from Baseline		SAC
2.23.	Safety	LB1	Summary of Urine Concentration Values		SAC
2.13.	Safety	LB16	Summary of Urinalysis by Maximum Grade Increase Post- Baseline Relative to Baseline		SAC
ECG					
2.14.	Safety	SAFE_T1	Summary of ECG Findings		SAC
2.15.	Safety	EG2	Summary of ECG Changes from Baseline		SAC
2.24	Safety	EG2	Summary of ECG Values		SAC
2.16.	Safety	EG10	Summary of Maximum QTc Values Post-Baseline Relative to Baseline by Category		SAC
2.17.	Safety	EG11	Summary of Maximum Increase in QTc Values Post-Baseline Relative to Baseline by Category		SAC
Vital Si	gns				•
2.18.	Safety	VS1	Summary of Vital Sign Changes from Baseline		SAC
2.25.	Safety	VS1	Summary of Vital Sign Values		SAC

Safety:	Safety: Tables					

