# **11.9.11. ICH Listings**

ICH: Li	stings				
No.	Population	IDSL / Example Shell	Title	Programming Notes	Deliverable [Priority]
Subjec	Disposition				
1.	Safety	ES3	Listing of Reasons for Study Withdrawal		SAC
2.	Safety	SD2	Listing of Reasons for Study Treatment Discontinuation		SAC
3.	Screened	ES7	Listing of Reasons for Screen Failure		SAC
Protoc	ol Deviations			•	
4.	Safety	DV2	Listing of Important Protocol Deviations		SAC
5.	Safety	IE3	Listing of Subjects with Inclusion/Exclusion Criteria Deviations		SAC
Popula	tions Analyzed			•	
6.	Safety	SP3A	Listing of Subjects Excluded from Any Population		SAC
Demog	raphic and Bas	seline Characteris	tics		
7.	Safety	DM2	Listing of Demographic Characteristics		SAC
8.	Safety	DM9	Listing of Race		SAC
Prior a	nd Concomitar	nt Medications		•	
9.	Safety	CM5	Listing of Concomitant Medications	Based on GSK Drug Dictionary	SAC
Exposi	ire and Treatm	ent Compliance			
10.	Safety	EX4	Listing of Exposure Data		SAC
11.	Safety	POP_L1	Listing of Meal Data		SAC
Advers	e Events				
12.	Safety	AE2	Listing of Relationship Between System Organ Class and Verbatim Text		SAC
13.	Safety	AE7	Listing of Subject Numbers for Individual Adverse Events		SAC

ICH: Li	stings				
No.	Population	IDSL / Example Shell	Title	Programming Notes	Deliverable [Priority]
14.	Safety	AE9CP	Listing of All Adverse Events		SAC
42.	Safety	AE9CP	Listing of Adverse Events of Special Interest		SAC
Serious	s and Other Sig	nificant Adverse	Events		
15.	Safety	AE9CP	Listing of Study Drug Related Adverse Events		SAC
16.	Safety	AE9CP	Listing of Serious Adverse Events (Fatal & Non-Fatal)		SAC
17.	Safety	AE14	Listing of Reasons for Considering as a Serious Adverse Event		SAC
18.	Safety	AE9CP	Listing of Adverse Events Leading to Withdrawal from Study		SAC
19.	Safety	PREG1b	Listing of Subjects Who Became Pregnant During the Study		SAC
Hepato	biliary (Liver)				
20.	Safety	MH2	Listing of Medical Conditions for Subjects with Liver Stopping Events		SAC
21.	Safety	SU2	Listing of Substance Use for Subjects with Liver Stopping Events		SAC
43	Safety	VS5	Listing of Vital Results for Subjects with Liver Stopping Events		SAC
44	Safety	LIVER5	Listing of Subjects with Liver Monitoring/Stopping Event Reporting		SAC
All Lab	oratory	1			
22.	Safety	LB5A	Listing of Clinical Chemistry with any Toxicities		SAC
23.	Safety	LB5A	Listing of All Clinical Chemistry Data for Subjects with any Toxicities		SAC
24.	Safety	LB5A	Listing of Hematology with any Toxicities		SAC

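### If direct bilirubin is measured, the SAP's lab-grading rule makes every value above ULN Grade 4, where the printed DAIDS row gives no grade without clinical signs (minor)

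*SAP*

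**What the plan says.** Section 11.6.1 (Appendix 6) first names the standard: "Laboratory abnormalities will be graded according to the DAIDS grading table Version 2.1, July 2017". It then sets two programming rules. The first drops any non-numeric condition: "only the numeric part of the criteria will be used". The second resolves ties: "If for a laboratory parameter there are multiple grades sharing the same criteria, the maximum grade will be used".

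The direct bilirubin row of the clinical chemistry table that follows has NA for Grades 1 and 2. Grade 3 is "> ULN with other signs and symptoms of hepatotoxicity" and Grade 4 is "> ULN with life-threatening consequences". No exception is made for this row.

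The grades feed Table 2.8, "Summary of Clinical Chemistry Results by Maximum Grade Increase Post-Baseline Relative to Baseline", and may feed Listing 22, "Listing of Clinical Chemistry with any Toxicities", and its companion Listing 23. The shells of those listings are not shown.

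The SAP does not say whether direct bilirubin is assayed. The Time and Events Table in Section 11.1.1 leaves the list of tests to Protocol Appendix 2, and the liver tests named for plotting in Section 9.2 include total but not direct bilirubin.

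**The concern.** In this row the clinical condition alone separates no grade, Grade 3 and Grade 4. Removing it leaves the same numeric limit in both graded cells, and the tie rule then selects the higher. The result disagrees with the table that the same paragraph says is being applied: a trivial, symptom-free excursion above ULN takes the grade the row reserves for life-threatening consequences.

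At stake is how the chemistry grade summary reads. In Table 2.8 such a value would appear as a jump from no grade to the highest grade. The amended SAP added liver-event summaries, liver-test plots and PK boxplots by ALT category, so liver results will be read closely and a spurious Grade 4 liver analyte would mislead.

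**Working it through.** **Inputs.** The two rules and the direct bilirubin and total bilirubin rows come from Section 11.6.1. Chemistry baselines are Day 1 for Treatment A and Day 10 for Treatment B (Section 5.2; the Time and Events Table footnote agrees: "Assessments performed on Day 10 will be considered Baseline for GSK3640254 dosing"). The scheduled laboratory days after those baselines are Day 10 for Treatment A and Days 21 and 24 for Treatment B. The SAP gives no figure of its own to reproduce here.

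**Step 1: apply the rule.** Let x be direct bilirubin divided by ULN. With clinical conditions removed, Grade 3 is x > 1 and Grade 4 is x > 1; the maximum is Grade 4. Total bilirubin at the same multiple is shown for scale.

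| x | SAP rule | Printed row, no clinical signs | Printed row, hepatotoxicity signs | Printed row, life-threatening | Total bilirubin at same multiple |
|---|---|---|---|---|---|
| 0.9 | none | none | none | none | none |
| 1.0 | none | none | none | none | none |
| 1.01 | 4 | none | 3 | 4 | none |
| 1.05 | 4 | none | 3 | 4 | none |
| 1.5 | 4 | none | 3 | 4 | 1 |
| 3 | 4 | none | 3 | 4 | 3 |

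Total bilirubin reaches Grade 4 only at 5.0 x ULN.

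**Step 2: look for other rows the tie sentence could serve.** The appendix prints 6 hematology + 23 chemistry + 3 urinalysis = 32 rows. Direct bilirubin is the only one in which two grades share a numeric limit.

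**Step 3: how often this would happen by chance.** Table 2.8 counts increases from baseline, so a spurious entry needs a baseline at or below ULN and at least one later value above it. Assume no drug effect, values normal on some scale, ULN at population quantile q, and equal correlation r between any two visits of one person. None of these is in the SAP. With z the normal quantile of q and k post-baseline visits:

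P(new Grade 4) = q - P(all k + 1 values ≤ z)

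At r = 0 this is q - q^(k+1). For q = 0.975 and k = 2: 0.975 - 0.975^3 = 0.975 - 0.9269 = 0.0481. For r > 0 the second term is the equicorrelated multivariate normal probability, obtained numerically.

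| Treatment, visits | ULN quantile q | r = 0 | r = 0.5 | r = 0.9 |
|---|---|---|---|---|
| B, Days 21 and 24 (k = 2) | 0.95 | 9.3% | 6.8% | 3.0% |
| B, Days 21 and 24 (k = 2) | 0.975 | 4.8% | 3.8% | 1.7% |
| B, Days 21 and 24 (k = 2) | 0.99 | 2.0% | 1.6% | 0.8% |
| A, Day 10 (k = 1) | 0.975 | 2.4% | 2.0% | 1.0% |

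These are chances per participant. Unscheduled repeats, which Section 11.3.2 admits for worst-case values, are not counted and could only raise them.

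**The case against.** The strongest reply is that this is a disclosed convention. Section 11.6.1 does not promise to apply each row in full, a laboratory value cannot show clinical signs, and some convention is therefore needed. The tie sentence has no other evident target, so it was probably written for this row, and it errs towards over-grading. That explains the rule but does not rescue it. The same paragraph says grading follows DAIDS, and for this row the rule returns a grade that the printed criterion does not support.

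Second, the point may not apply. The test list is in the protocol, only total bilirubin is plotted, and the appendix also prints a male-only hemoglobin row in a study of female participants, so a printed row does not prove an assay. This stands, and the finding is conditional for that reason.

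Third, the frequencies rest on assumptions, and the Treatment B range of 0.8% to 9.3% spans more than tenfold. This also stands. The contradiction in Step 1 needs none of those assumptions.

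Fourth, withholding a grade departs from the printed row in the other direction, because a participant with hepatotoxicity would get no direct bilirubin grade where the row gives 3 or 4. That is true. But the row cannot be applied from the laboratory value alone, and such cases would be expected in the AE and liver-event displays. The shells of those displays are not shown, so their content cannot be confirmed here.

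**Conclusion.** The concern holds, as a minor point. If direct bilirubin is assayed, the rule assigns Grade 4 to every value above ULN, makes Grade 3 unattainable, and contradicts the printed row for every symptom-free value above ULN. That result is deterministic and follows from the SAP's text.

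How often it would arise is uncertain. Under the stated assumptions, and with no drug effect, the central case for Treatment B is 1.7% to 4.8% per participant, depending on within-person correlation.

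The reach is narrow: Table 2.8 and possibly Listings 22 and 23. The primary PK analysis, the AE and SAE displays, and the separately defined liver displays (Tables 2.26 and 2.27, Figures 2.2 to 2.6, Listing 44) are not shown to be affected. Actual chemistry values are summarized separately in Table 2.21.

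**What to change.** Check Protocol Appendix 2 for direct bilirubin.

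- **If it is assayed:** add one sentence to Section 11.6.1 exempting it from the numeric-part and maximum-grade rules and stating that no DAIDS grade is assigned from the laboratory value alone. Report values above ULN as an ungraded high flag against the normal range, outside the grade-increase counts of Table 2.8. Section 11.4.1 already uses High and Low normal-range categories. Clinical hepatotoxicity stays in the existing AE and liver-event displays, and no new adjudication is needed.
- **If it is not assayed:** delete the row and the tie sentence. No other printed row needs that sentence.

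The cost is one sentence in Appendix 6 and one exception in the grading program.

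### SAP Appendix 6: the two lines of the Grade 3 low-bicarbonate cell disagree (upper limit 11.0 in mEq/L, 110 in mmol/L), and the SI line is the one used for grading

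*SAP*

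**What the plan says.** SAP section 11.6.1 sets out how laboratory results are graded:

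- Source: "Laboratory abnormalities will be graded according to the DAIDS grading table Version 2.1, July 2017". Section 9.2 names the same version.
- Units: "Laboratory results are converted to use SI units; only the numeric part of the criteria will be used".
- Ties: "If for a laboratory parameter there are multiple grades sharing the same criteria, the maximum grade will be used".

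The row at issue is headed "Bicarbonate, Low (mEq/L; mmol/L"), and each cell gives one line per unit:

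- Grade 1: "16.0 to < LLN 16.0 to < LLN"
- Grade 2: "11.0 to < 16.0 11.0 to < 16.0"
- Grade 3: "8.0 to < 11.0 8.0 to < 110"
- Grade 4: below 8.0 on both lines.

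The chemistry grades feed Table 2.8 (largest grade increase over baseline, section 11.9.5) and Listings 22 and 23 (chemistry toxicities, and all chemistry data for participants who have one, section 11.9.11). Section 5.2 takes the chemistry baseline from Day 1 pre-dose for Treatment A and from Day 10 for Treatment B.

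**The concern.** Grade 3 is the only cell in the row whose two lines differ. Its SI upper limit runs past the Grade 2 and Grade 1 bands and past any plausible normal range, which cannot be intended for a criterion on low values. The units rule makes the SI line the operative one, so the error is not confined to a line that nobody uses.

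What is at stake is the graded reporting of one chemistry analyte. A program written straight from the SI line would put participants with normal bicarbonate in Grade 3 at baseline and would list them as having a toxicity. Table 2.8 would then have little room to show a worsening after GSK3640254 is added.

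**Working it through.** **Inputs.** The limits are those printed in section 11.6.1. The SAP gives no LLN for bicarbonate, so I assume 20, 22 and 23 mmol/L in turn, and I test values up to 32 mmol/L as normal. Both are assumptions.

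**Step 1: unit check.** mmol/L = mEq/L ÷ valence. Bicarbonate has valence 1, so 11.0 mEq/L ÷ 1 = 11.0 mmol/L. The printed SI limit is 110, and 110 ÷ 11.0 = 10. The printed SI figure is therefore not reproduced.

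**Step 2: continuity check.** Grade 2 starts at 11.0 and Grade 4 ends at 8.0. A Grade 3 band of 8.0 to < 11.0 fills the gap exactly. A band of 8.0 to < 110 overlaps Grade 2 (11.0 to < 16.0), Grade 1 (16.0 to < LLN) and everything from LLN to below 110.

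**Step 3: apply both readings.** Grades met, with an assumed LLN of 22 mmol/L:

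| Value (mmol/L) | Limit 11.0 | Limit 110 as printed |
|---|---|---|
| 7 | 4 | 4 |
| 8 | 3 | 3 |
| 10.9 | 3 | 3 |
| 11 | 2 | 2 and 3 |
| 15.9 | 2 | 2 and 3 |
| 16 | 1 | 1 and 3 |
| 21 | 1 | 1 and 3 |
| 22 | none | 3 |
| 24 | none | 3 |
| 32 | none | 3 |

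Changing the LLN to 20 or 23 moves only the values next to it: at LLN 20, 21 becomes ungraded, or Grade 3 as printed; at LLN 23, 22 becomes Grade 1, or Grades 1 and 3 as printed. Values from 24 to 32 give the same result for all three LLNs. With 11.0, no value meets two grades and no normal value is graded.

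**Step 4: does the tie rule settle the overlaps?** It covers grades whose criteria are the same. Direct bilirubin is such a case: Grade 3 is "> ULN with other signs and symptoms of hepatotoxicity", and once the text is dropped Grades 3 and 4 both reduce to a value above ULN. The ranges 11.0 to < 16.0 and 8.0 to < 110 overlap but are not the same criterion. As printed, a value of 14 mmol/L therefore has no determined grade. A normal value does not need the rule, because it meets Grade 3 alone.

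**Step 5: effect on the displays under literal coding.** Take a participant who falls from 24 to 14 mmol/L. With 11.0 she goes from ungraded to Grade 2, and Table 2.8 shows an increase. As printed she starts at Grade 3 and ends at Grade 2 or Grade 3, depending on how the overlap is coded; neither is an increase. From a normal baseline, only a fall below 8.0 (Grade 4) would count as one. Listings 22 and 23 would take in every participant with a bicarbonate result below 110 mmol/L.

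**The case against.** The strongest reply is that nobody would apply this cell as printed. The plan names DAIDS Version 2.1 as its grading source, the row concerns low values, the line above in the same cell says 11.0, and Grade 2 starts at 11.0. Grading healthy volunteers as Grade 3 at baseline would also be noticed in the first output. This stands as a reason to call the point minor. It does not make the entry right: the SAP reprints the limits with its own units rule, and a programmer may well work from that reprint.

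Three further points stand:

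- A PDF-reading artefact cannot be excluded. The same table has a garbled label in the high-sodium row and a point in place of a comma in a triglyceride limit. Against this, 110 followed by a point has every character of 11.0 with only the point moved, which looks more like a typing slip. The text alone cannot settle it.
- The SAP does not show that bicarbonate is assayed. Appendix 6 also carries male-only haemoglobin limits although the study enrols women, so the presence of a row proves little.
- Falls in bicarbonate would remain visible in Table 2.7 (changes from baseline) and Table 2.21 (values), which do not use grades.

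Two stronger readings are tempting. One is that the SAP's rules turn every normal bicarbonate into a Grade 3 toxicity, with the tie rule sending overlapping values to the highest grade. The document does not support this: the tie rule does not cover overlapping ranges, and the cited DAIDS table and the rest of the row contradict the printed figure. The other is that real falls in bicarbonate would be hidden. The ungraded tables rule that out.

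**Conclusion.** This is a minor but real inconsistency in an operative criterion. The SI limit for Grade 3 low bicarbonate is ten times its counterpart in the same cell. The consequence is conditional on three things: the source document really prints 110, bicarbonate is among the analytes measured, and the SI line is coded without checking it against the rest of the row or DAIDS. If all three hold, the graded displays (Table 2.8, Listings 22 and 23) are wrong for this one analyte. The finding for values of 24 mmol/L and above does not depend on which LLN from 20 to 23 mmol/L is assumed. The PK and PD analyses are not touched.

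**What to change.** 1. Check the source PDF of the SAP to confirm that the printed figure is 110.
2. If so, change the SI upper limit of Grade 3 low bicarbonate to < 11.0, so that it agrees with the mEq/L line of its own cell, and verify it against the cited DAIDS Version 2.1 table.
3. Check the limit in the grading code behind Table 2.8 and Listings 22 and 23. If bicarbonate is not assayed, the code check can be skipped.

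The cost is one corrected figure and one look at the code. I see no downside.
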